1.4 Rationale for study

The UK National Screening Committee has recommended that further research is required into alternative screening tests before a population-based prostate cancer screening programme can be considered for approval(42). We propose that prostate MRI has certain performance characteristics, which make it attractive as a potential screening test. We have previously shown that prostate is a reliable pre-biopsy triage test in secondary care once

IP1 - PROSTAGRAM	Protocol No: 18HH4595	Sponsor: Imperial College London	V 1.2 01MAY2019
-------------------------	---------------------------------	--	------------------------

men have been referred to hospitals for an elevated serum PSA. However, its role as a screening test is unknown and warrants further investigation.

Our long-term objective is to evaluate whether a screening prostate MRI could be an alternative or complementary image-based screening test to PSA.

The current study has not been designed to establish the sensitivity and specificity of MRI as this would require all participants to undergo a prostate biopsy as the reference standard for determining the presence of prostate cancer. It would not be appropriate in a screening study to require all participants to have a biopsy particularly when the diagnostic performance of prostate MRI has been well established in secondary care with prostate biopsy as the reference standard.

Instead, the primary objective will be to establish the prevalence of screen-positive prostate MRI in the general male population aged 50-69 years and collect information on the feasibility of a larger scale study. The results of this study will inform the design of a large diagnostic paired cohort validating study comparing PSA and MRI and other potential imaging or fluidic biomarkers. The subsequent study requires a large sample size and resource commitment due to the low prevalence of prostate cancer in a screened population. In this study, we will obtain point estimates on the prevalence of a suspicious test that triggers a biopsy; such information is currently not available and is required to inform the design and sample size calculations of the larger clinical study. This study will also evaluate the feasibility of a large screening MRI trial. We will optimise recruitment strategies and identify potential barriers to recruitment.

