5.3.2 Randomisation of screening tests

In order to allow to limit reporter/reviewer bias all screening test will be interpreted by an independent assessor blinded to the results of the other tests. In particular, the MRI and US report will be issued prospectively prior to any prostate biopsy. The pathologist will be blinded to the results of imaging/PSA.

It is not practical to fully blind the biopsy surgeon to the results of the screening tests, as the procedure will vary dependent on whether there is a lesion on the image-screening test. Therefore, the study team will inform the biopsy surgeon whether targeting needs to be incorporated into the biopsy strategy and the location of any areas suspicious on imaging. This need for biopsy also means that it will not be feasible to fully blind participants to their screening result. However, if participants are informed of all their results this a potential source of attrition bias if participants selectively withdraw from undergoing biopsy based on the results of a single test. Participants may place undue emphasis on the image based screening tests at the expense of the PSA or biomarker test. To reduce the risk of selective withdrawal men who are recommended for biopsy will be informed that one or more of their screening test is positive. However, the specific test indicating a biopsy will not be made available to participants until after the prostate biopsy. Men who have a complete set of negative screening tests will be informed that no biopsy is required.

Men will be unblinded to the screening test results after having a biopsy or on exiting the trial due to negative screening tests. If a participant withdraws from the trial, they will be unblinded to their screening test result. There should be no other reasons for unblinding during the study.

PROSTAGRAM	Protocol no: 18HH4595	Sponsor: Imperial College London	V 1.01MAY2019
-------------------	---------------------------------	---	----------------------

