### 8.2. Definition of a Positive Screening Test

Men will proceed to biopsy if any of the screening tests are positive. This includes:

[figure not shown]
- PSA: A raised PSA is defined as  $PSA \geq 3.0$ ng/ml as per UK screening guidelines.
- MRI: The presence of a discrete radiological score 3, 4 or 5 as scored by a radiologist or lesion on CAD/AI.
- Ultrasound: The presence of a discrete score of 3, 4 or 5 or prostate lesions on ultrasound.

Further threshold definitions for a screen-positive result for MRI and ultrasound will be analysed, as outlined in Sections 10.3.1 and 10.3.2.

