##### PIRADS:

1. The presence of a discrete PIRADS score 3, 4 or 5 as scored by a radiologist.
2. The presence of a discrete PIRADS score 4 or 5 as scored by a radiologist.

Analysis of the primary end point will be repeated using each screen-positive cut-off definition, for both MRI scoring systems. Analyses of all other end points will be repeated for the two cut-offs defined by the PIRADS scoring system only. A biopsy will be carried out if at least one of the scores is screen-positive, even if there is disagreement between the scores.

The radiologist will report whether the MRI result was screen-positive or negative based on the PIRADS and Likert scores for each lesion.

If the question “Are there any lesions with an MRI score  $\geq 3$ ?” is recorded as “No”, on the MRI Reporting Form eCRF, then the MRI score (for both the Likert and PIRADS scoring systems) is classified as 1 or 2. This result would be categorised as a screen-negative result when using the first cut-offs for the two scoring systems above.

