----------------------------------	---------------------------	------------

	
 
Proportion within each value of US score detected to have each type of clinical cancer (Sections 8.1 & 10.3.2)
 
Histograms of distribution of type of cancer detected across scoring systems
 
	respective analyses 
Proportion of participants with raised and normal PSA level with no cancer, insignificant cancer and significant cancer	Proportion with raised and normal PSA result detected to have each type of clinical cancer (Sections 8.1 & 10.3.3)	Participants biopsied, and who have PSA results 
Comparison of the proportion of participants with a positive result for each screening test	
Comparisons of proportions of results (positive/negative) between pairs of screening tests:
 
 
MRI & ultrasound
 
MRI & PSA
 
Ultrasound & PSA
 
 
using McNemar chi square tests
	Participants who completed both tests in each pair 
Comparison of the proportion of men subsequently diagnosed with a clinically significant prostate cancer (as defined by pre-specified histological definitions)	
 
Sensitivity and specificity of screening results (MRI, ultrasound and PSA) with histology results as reference standard (Sections 10.3.1, 10.3.2 and 10.3.3)
 
Graph displaying proportions of results for each screening test compared to histology results
 
Proportions of false positive results by each screening test (MRI, ultrasound and PSA), using histology (no cancer) as the reference
 
Proportions of false positive results by each screening test (MRI, ultrasound and PSA), using histology (no cancer or Gleason 3+3) as the reference
 
	Participants biopsied, and who completed the relevant test for the respective analysis 

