Sensitivity and specificity analysis will be conducted between screening test results and histology results (reference standard). Histology results will be dichotomised into "clinically significant cancer" and "absence of clinically significant cancer" (repeated for each of the threshold definitions in Section 8.1). The following measures of test accuracy will be reported, along with

Imperial Clinical Trials Unit	STATISTICAL ANALYSIS PLAN	PROSTAGRAM
----------------------------------	---------------------------	------------

their 95% confidence intervals: negative predictive value (NPV), positive predictive value (PPV), sensitivity and specificity. Results will be displayed using graphs for each screening test.

The proportions of false positive results will be reported, with histology as reference. This analysis will be repeated for each of the definitions of false positive results outlined in Section 10.3.8.

For each HDP (see Section 8.3) the proportion of participants with all positive tests, along that pathway, will be reported. For each HDP, we will take the population of participants with all positive tests along each pathway and provide summary statistics. Screen-positive results for MRI are defined by PIRADS cut-off [2] in Section 10.3.1. Similarly, screen-positive results for ultrasound are defined by US cut-off [2] in Section 10.3.2. A “positive” PSA result is defined by a raised PSA level ( $\geq 3.0\text{ng/ml}$ ) (see Section 10.3.3). The summary statistics will be in terms of: the total number of patients who were biopsied (see Section 10.3.5), the total number of patients who were detected to have clinically insignificant cancer in targeted and non-targeted cores, separately, and, the total number of patients who were detected to have clinically significant cancer in targeted and non-targeted cores, separately. This analysis will be limited to the generally accepted definitions for the detection of clinically significant and insignificant cancers (definitions (i) in Sections 8.1.1 & 8.1.2) (7), only.

The proportions of patients, with positive test results by each screening test, who go onto local or systemic treatment for prostate cancer (see Section 10.3.6) will be reported. Positive screening test results will be defined using the PSA cut-off in Section 10.3.3, and both PIRADS and US cut-offs in Sections 10.3.1 & 10.3.2.

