MRI	Positive MRI (PIRADS ≥ 3) (Cut-off [1])			McNemar's chi2(1) = xx.xx p-value = x.xxx	McNemar's chi2(1) = xx.xx p-value = x.xxx	McNemar's chi2(1) = xx.xx p-value = x.xxx
	Positive MRI (PIRADS ≥ 4) (Cut-off [2])			McNemar's chi2(1) = xx.xx p-value = x.xxx	McNemar's chi2(1) = xx.xx p-value = x.xxx	McNemar's chi2(1) = xx.xx p-value = x.xxx
Ultrasound	Positive ultrasound (US ≥ 3) (Cut-off [1])	McNemar's chi2(1) = xx.xx p-value = x.xxx	McNemar's chi2(1) = xx.xx p-value = x.xxx			McNemar's chi2(1) = xx.xx p-value = x.xxx
	Positive ultrasound (US ≥ 4) (Cut-off [2])	McNemar's chi2(1) = xx.xx p-value = x.xxx	McNemar's chi2(1) = xx.xx p-value = x.xxx			McNemar's chi2(1) = xx.xx p-value = x.xxx
PSA	Raised PSA (≥ 3.0 ng/ml)	McNemar's chi2(1) = xx.xx p-value = x.xxx	McNemar's chi2(1) = xx.xx p-value = x.xxx	McNemar's chi2(1) = xx.xx p-value = x.xxx	McNemar's chi2(1) = xx.xx p-value = x.xxx	

See Section 10.3.1, 10.3.2 and 10.3.3 for definitions

Screen-positive vs screen-negative results by each threshold definition

**Table 1.2. 11: Sensitivity and specificity of screening results (screen-positive or screen-negative) with histology results (clinically significant cancer vs absence of clinically significant cancer) as reference standard**

	Screening results
--	--------------------------------------

		Positive MRI (PIRADS $\geq 3$ ) (Cut-off [1])	Positive MRI (PIRADS $\geq 4$ ) (Cut-off [2])	Positive ultrasound (US $\geq 3$ ) (Cut-off [1])	Positive ultrasound (US $\geq 4$ ) (Cut-off [2])	Raised PSA ( $\geq 3.0$ ng/ml)
Prevalence		xxx (xx%)	xxx (xx%)	xxx (xx%)	xxx (xx%)	xxx (xx%)
Definitions of clinically significant cancer	i	Sens = Spec = PPV = NPV =	Sens = Spec = PPV = NPV =	Sens = Spec = PPV = NPV =	Sens = Spec = PPV = NPV =	Sens = Spec = PPV = NPV =
	ii	Sens = Spec = PPV = NPV =	Sens = Spec = PPV = NPV =	Sens = Spec = PPV = NPV =	Sens = Spec = PPV = NPV =	Sens = Spec = PPV = NPV =
	iii	Sens = Spec = PPV = NPV =	Sens = Spec = PPV = NPV =	Sens = Spec = PPV = NPV =	Sens = Spec = PPV = NPV =	Sens = Spec = PPV = NPV =
	iv	Sens = Spec = PPV = NPV =	Sens = Spec = PPV = NPV =	Sens = Spec = PPV = NPV =	Sens = Spec = PPV = NPV =	Sens = Spec = PPV = NPV =
	v	Sens = Spec = PPV = NPV =	Sens = Spec = PPV = NPV =	Sens = Spec = PPV = NPV =	Sens = Spec = PPV = NPV =	Sens = Spec = PPV = NPV =

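### Sensitivity, specificity and NPV are computed in biopsied men only but labelled test accuracy; at the ≥3 cut-offs this understates specificity, for MRI by about 26–39 points or 28–29 points depending on the protocol's MRI scenario

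*SAP*

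**What the plan says.** SAP 11.2.3: "Sensitivity and specificity analysis will be conducted between screening test results and histology results (reference standard"). It continues: "The following measures of test accuracy will be reported, along with" 95% intervals, and names NPV, PPV, sensitivity and specificity. SAP Table 1 gives the population as "Participants biopsied, and who completed the relevant test for the respective analysis". The Table 1.2.11 shell is titled "Sensitivity and specificity of screening results (screen-positive or screen-negative) with histology results" and covers PIRADS ≥3 and ≥4, ultrasound ≥3 and ≥4, and PSA ≥3.0 ng/ml, each under five cancer definitions.

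Biopsy follows any positive test. For MRI, SAP 8.2 defines this as "The presence of a discrete radiological score 3, 4 or 5 as scored by a radiologist or lesion on CAD/AI". SAP 10.3.1 makes Likert a further route: "A biopsy will be carried out if at least one of the scores is screen-positive, even if there is disagreement between the scores". Ultrasound and PSA are the other triggers. For everyone else, Protocol 5.3.2 says: "Men who have a complete set of negative screening tests will be informed that no biopsy is required".

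Protocol 1.4 states the limitation: "The current study has not been designed to establish the sensitivity and specificity of MRI as this would require all participants to undergo" a biopsy. SAP 2.6 restates the rationale without that sentence. SAP 12 expects little missing data and probably no imputation.

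**The concern.** At the ≥3 cut-offs every MRI-positive man is due for biopsy, so MRI false positives are counted. An MRI-negative man has histology only if another trigger fired, so most true negatives drop out and specificity falls. How far it falls depends on how often the other tests are positive, so the reported figure is not a property of MRI alone. The same applies to ultrasound and PSA. The MRI-negative men who remain were selected by a positive PSA, ultrasound or other trigger, which affects NPV. Cancers negative on every trigger are not in the data, which raises sensitivity.

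These figures are destined for the primary outcome paper, from a study meant to inform a larger comparative one. Printed as test accuracy with confidence intervals, they would misdescribe how the tests behave in screened men.

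**Working it through.** **Plan's own figures.** Protocol 9.1 has 10.4% raised PSA with 73% MRI-positive, and 89.6% normal PSA with 2.2% significant cancer. MRI sensitivity/specificity is 74%/88% from a meta-analysis (scenario A) or 93%/41% from a paired validating study (scenario B). A: 0.896 × 0.1337 + 0.104 × 0.73 = 0.196, and 1.96² × 0.196 × 0.804 / 0.05² = 242.1, so 243. B: 0.611 gives 365.2, so 366. Both reproduce.

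**Two readings at raised PSA.** Protocol 9.1 fixes MRI positivity there at 73% (Group 1), and also assumes the same MRI sensitivity and specificity at raised and normal PSA (Group 2, item 2a). Both hold together only if significant cancer at raised PSA is (0.73 − 0.12)/(0.74 − 0.12) = 98% in A, or (0.73 − 0.59)/(0.93 − 0.59) = 41% in B. I therefore show both readings.

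**Assumed, not in the documents.** Significant cancer at raised PSA 10–41%; ultrasound 84%/86% (Protocol 1.2.2, published for any cancer) applied to significant cancer; MRI and ultrasound independent given disease; full biopsy uptake; no extra Likert or CAD/AI biopsies.

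**Counts, N = 366.** Raised PSA: 38.1 men. Normal PSA: 327.9 men, 7.2 with and 320.7 without significant cancer. All raised-PSA men are biopsied. At normal PSA, the biopsied MRI true negatives are 320.7 × sp(MRI) × (1 − sp(US)).

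Worked case: A, 73% held, 10% cancer at raised PSA (3.8 with, 34.3 without).
- Raised PSA: MRI positives 0.73 × 38.1 = 27.8; TP 0.74 × 3.8 = 2.8; FP 25.0; TN 9.3.
- Normal PSA: FP 0.12 × 320.7 = 38.5; TN 282.2, of whom 0.14 × 282.2 = 39.5 are biopsied.
- Biopsied men: 48.8/(48.8 + 63.5) = 0.435. All men: (9.3 + 282.2)/355.0 = 0.821.

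| MRI ≥3 | Biopsied | Specificity, biopsied | Specificity, all men |
|---|---|---|---|
| A, 73% held | 123 | 0.43–0.46 | 0.82–0.84 |
| A, same accuracy | 123 | 0.59–0.62 | 0.88 |
| B, either reading | 253 | 0.12–0.13 | 0.40–0.41 |

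The loss is 26–39 points in A and 28–29 in B. Exact 95% intervals in A exclude the all-men value either way: 49/112 gives 0.34–0.53 (73% held), and 63/105 gives 0.50–0.69 (same accuracy, 30% cancer at raised PSA).

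**Other measures.**
- Ultrasound specificity: 0.52–0.56 (A) and 0.79 (B), against 0.86.
- PSA specificity: 0.69–0.78 (A) and 0.86–0.90 (B), against 0.90–0.93.
- MRI NPV, 73% held: 0.89–0.95 against 0.98–0.99 (A); 0.95–0.98 against 0.99 (B).
- MRI sensitivity: 0.3–2 points too high if misses are independent. If MRI and ultrasound miss the same cancers as far as their sensitivities allow, it is 0.78–0.83 against 0.74 (A) and 0.95–0.97 against 0.93 (B).

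**Robustness, 73% held.**
- From no overlap to maximum overlap of MRI and ultrasound false positives at normal PSA, reported MRI specificity runs from 0.48 down to 0.19 (A) and 0.21 down to 0.04 (B).
- Ultrasound specificity of 0.70 or 0.95 moves it in A to 0.60–0.62 or 0.27, while the all-men value stays at 0.82–0.84.
- If 5–10% of MRI-negative, normal-PSA men were also biopsied through Likert or CAD/AI (assumed), it would be 0.49–0.56 (A) and 0.14–0.16 (B).

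**Putting the unbiopsied men back.** With significant-cancer prevalence of 0%, 0.5% and 2.2% in unbiopsied men (243 in A, 113 in B), MRI specificity stays at 0.82–0.84 or 0.88 in A, by reading, and near 0.40 in B. Sensitivity goes 0.75–0.76, 0.68–0.71, 0.51–0.61 in A, and 0.93–0.94, 0.89–0.91, 0.76–0.84 in B.

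**The case against.** The population is not hidden: Table 1 states it, and histology as reference standard implies it. Protocol 1.4 explains the limitation. These are secondary estimates in a study sized on MRI positivity. Much of what a reader needs is already planned: positive rates (Table 1.2.2), cancer by score or PSA level (Tables 1.2.7–1.2.9), false positives by test and cut-off (Tables 1.2.12–1.2.13), and screen-positive and biopsied rows by pathway (Table 1.2.14). All of this stands and lowers the severity. It does not change what is computed, and neither 11.2.3 nor Table 1.2.11 repeats the restriction or the caveat.

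A reader might infer more than the documents support:
- *A single loss of about 39 points for MRI.* In A that needs 73% positivity held at raised PSA, which implies MRI specificity there of 0.27–0.28 and conflicts with the equal-accuracy assumption. Under equal accuracy the loss is 26–29 points.
- *MRI is the test most affected.* Under equal accuracy in A, ultrasound loses 30–34 points. At ultrasound specificity 0.70 with 73% held, ultrasound loses 38–41 and MRI about 22.
- *NPV is always too low.* If neither PSA nor ultrasound carried information on disease, NPV would be unbiased (0.993 against 0.993). The protocol's inputs imply that they do.
- *Cancers missed by every test can never be seen.* Protocol 5.5 allows optional linkage for interval cancers. It depends on consent and funding, and SAP 4.2.5 places linkage outside the SAP, so it does not repair this analysis.

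**Conclusion.** The point holds. At the ≥3 cut-offs, MRI specificity in biopsied men is well below its value in screened men in every scenario built on the protocol's inputs: by 26–39 points in A, depending on the reading, and 28–29 in B. Ultrasound and PSA specificity are about 30–34 and 16–21 points too low in A, and about 7 and 3–5 in B, at ultrasound specificity 0.86. Which test suffers most depends on the assumptions. NPV is 1–9 points too low, given informative PSA or ultrasound. Sensitivity is too high by an unidentified amount.

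The ≥4 cut-offs should be less affected, because score-3 men are biopsied and count as negatives, but the documents give no score split to size it. PPV is unaffected if all positives are biopsied, and so is the primary endpoint. The sizes rest on the assumptions listed with the calculation; the direction for specificity survived every variation tried. Because these are secondary estimates, this should be fixed but does not threaten the study's main result.

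**What to change.** 1. In SAP 11.2.3, Table 1 and Table 1.2.11, label sensitivity, specificity and NPV as applying to biopsied men only and not as test accuracy in screened men. Carry over the Protocol 1.4 limitation. Keep PPV and the false-positive proportions.
2. If absolute accuracy is reported, calculate it in all screened men over a stated, assumed range of significant-cancer prevalence in unbiopsied men, for example 0%, 0.5% and 2.2%, plus a higher stress value. The 2.2% is not an upper bound: Protocol 9.1 says the sextant biopsy behind it underestimates by an unknown amount. State that specificity is stable over the range and that sensitivity is not identified.
3. For each test and cut-off, report significant cancers detected and false-positive biopsies per 100 men screened, with 95% intervals. Most of this can be derived from Tables 1.2.2, 1.2.7–1.2.9 and 1.2.12–1.2.13.
4. Extend the biopsy-uptake rows of Table 1.2.14, now at ≥4 only, to the ≥3 cut-offs, and add PSA alone.

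The cost is SAP wording and table-shell changes on data already collected, with no new participants or procedures. The downside is that the paper has no single headline accuracy figure.

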5.3 Randomisation and Blinding

5.3.1 Randomisation of Biopsy Lesion

If both the MRI and ultrasound are scored as suspicious by the relevant scoring system, these men will be randomised to have their ultrasound or MRI targeted biopsies first in order to reduce incorporation bias. This can occur as the biopsy tracts from the first lesion may influence the tracts of the second lesion.

Therefore, a pseudo-randomisation will be carried out by a random number generator in advance of the trial starting. Block randomization will be employed to keep the numbers in each group as similar as possible. A block size of 4 has been chosen to reduce the chances that the biopsy order is inadvertently guessed by the operators. Allocation will be held by the Imperial Clinical Trials Unit and the order for lesions to be biopsied passed to the operating surgeon before the procedure begins. No provision for out-of-hours randomization will be required for this study of elective procedures. Occasional audit of the demographic and other characteristics of the groups produced during the study will ensure a balance between the two groups.

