6.6 Prostate biopsy

Men will proceed to biopsy if any screening test is positive. This includes

- PSA: A raised PSA is defined as $PSA \geq 3.0 \text{ ng/ml}$ as per UK screening guidelines
- MRI: The presence of a discrete radiological score 3, 4 or 5 as scored by a radiologist or lesion on CAD/AI
- Ultrasound: The presence of prostate lesions on ultrasound

If there is a lesion detected on an image based screening test men will have image-fusion guided biopsies for each lesion detected under local anaesthetic or sedation. The targeted

PROSTAGRAM	Protocol no: 18HH4595	Sponsor: Imperial College London	V 1.01MAY2019
-------------------	---------------------------------	---	----------------------

biopsy procedure will follow a Standard Operating Procedure (SOP Prostate Biopsies). Men will have been randomised by means of random number generator result to have either their MRI or ultrasound derived lesions biopsies first in order to overcome incorporation bias affecting the biopsy procedure.

If no lesion is identified, men will have a systematic prostate biopsy as per the local centre standard of care pathway. Prostate biopsy tissues samples will be preserved in formalin as soon as they are taken. All biopsy samples will be transported to Imperial College Healthcare NHS Trust for processing. No additional samples will be taken beyond what is required for a clinical diagnosis as outlined in the biopsy SOP.

The prostate biopsy samples will be stored in Imperial College Healthcare NHS Trust pathology department for a period of 30 years of and destroyed as per the standard operating regulations of the NHS laboratories.

The prostate biopsy samples will be stored in Imperial College Healthcare NHS Trust pathology department for a period of 30 years of and destroyed as per the standard operating regulations of the NHS laboratories.

PROSTAGRAM	Protocol no: 18HH4595	Sponsor: Imperial College London	V 1.01MAY2019
-------------------	---------------------------------	---	----------------------

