### 10.3.5. Biopsy Rates

Biopsy rates will be the recorded number of patients who undergo the systematic prostate biopsy, and who undergo a targeted biopsy (MRI- and/or ultrasound-guided). The systematic biopsy will be carried out for any patient who attains at least one positive screening test (PSA, ultrasound or MRI). A MRI or ultrasound-guided biopsy will be carried out for patients who receive a positive screening result by the respective test.

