Screen-positive vs screen-negative using definitions in Sections 10.3.1, 10.3.2 and 10.3.3

Clinically significant cancer vs absence of clinically significant cancer. See Section 8.1 for threshold definitions

**Table 1.2. 12: Proportions of false positive results by each screening test (MRI, ultrasound and PSA) with histology (no cancer) as reference**

False positive results (histology as reference)	MRI (PIRADS) 		Ultrasound (US) 		PSA 
	Cut-off [1] ( $\geq 3$ )	Cut-off [2] ( $\geq 4$ )	Cut-off [1] ( $\geq 3$ )	Cut-off [2] ( $\geq 4$ )	Raised ( $\geq 3.0$ ng/ml)
Proportion – n (%)	xxx (xx%)	xxx (xx%)	xxx (xx%)	xxx (xx%)	xxx (xx%)
95% confidence interval	x.xx to x.xx	x.xx to x.xx	x.xx to x.xx	x.xx to x.xx	x.xx to x.xx

False positive results are defined as a screen-positive result when prostate cancer is not present on biopsy (no cancer found on biopsy) (see Section 10.3.8)

See Section 10.3.1, 10.3.2 and 10.3.3

**Table 1.2. 13: Proportions of false positive results by each screening test (MRI, ultrasound and PSA) with histology (no cancer or Gleason 3+3) as reference**

Imperial Clinical Trials Unit	STATISTICAL ANALYSIS PLAN	PROSTAGRAM
----------------------------------	---------------------------	------------

See Table 1.2. 12, but for false positive results, with histology as reference, defined as a screen-positive result when no prostate cancer or Gleason 3+3 is present on biopsy.

False positive results are defined as a screen-positive result when prostate cancer is not present on biopsy or Gleason 3+3 is present on biopsy

See Section 10.3.1, 10.3.2 and 10.3.3

Imperial Clinical Trials Unit	STATISTICAL ANALYSIS PLAN	PROSTAGRAM
-------------------------------	---------------------------	------------

**Table 1.2. 14: Comparison of different testing combinations in terms of biopsy rates, detection of clinically insignificant cancer, in targeted and non-targeted cores, and clinically significant cancer, in targeted and non-targeted cores**

		Hypothetical Diagnostic Pathways 						
		MRI 	Ultrasound 	PSA ( $\geq$ 1.0ng/ml) & MRI 	PSA ( $\geq$ 3.0ng/ml) & MRI 	PSA & Ultrasound 	Ultrasound  & MRI 	PSA & Ultrasound  & MRI 

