	Comparison of the proportion of participants with a positive result for each screening test	
 
• MRI score: 
 
• PIRADS score
 
• Binary recorded overall MRI score
 
 
 
• Ultrasound score: 
 
• US score
 
• Binary recorded overall US score
 
 
 
• Dichotomised PSA level
 
	Visit 1 PSA, MRI & US reporting forms
	Comparison of the proportion of men subsequently diagnosed with a clinically significant prostate cancer (as defined by pre-specified histological definitions).	
 
• MRI score: 
 
• PIRADS score
 
• Binary recorded overall MRI score
 
 
 
• Ultrasound score: 
 
• US score
 
• Binary recorded overall US score
 
 
 
• Dichotomised PSA level
 
• Type of clinical cancer diagnosed on biopsy (using all definitions in Section 8.1 using variables in Section 10.3.4)
 
• Pathology score (Gleason score) on biopsy
 
	Visit 1 PSA, MRI & US reporting forms Visit 2 Biopsy reporting form
	Comparison of different testing combinations in terms of biopsy rates, detection of clinically insignificant cancer and significant cancers	
 
• MRI score: 
 
• PIRADS score
 
• Binary recorded overall MRI score
 
 
 
• Ultrasound score: 
 
• US score
 
• Binary recorded overall US score
 
 
 
• PSA level
 
• For each of the screening test combinations: 
 
• Biopsy rates: recorded number of patients who undergo recommended biopsy (systematic and targeted) (Section 10.3.5)
 
 
 
	Visit 1 PSA, MRI & US reporting forms Visit 2 Biopsy reporting form

Imperial Clinical Trials Unit	STATISTICAL ANALYSIS PLAN	PROSTAGRAM
-------------------------------	---------------------------	------------

		
 
Type of clinical cancer diagnosed (using all definitions in Section 8.1 using variables in Section 10.3.4) for targeted and non-targeted cores
 
	

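### Table 1.2.14 pools MRI-targeted and ultrasound-targeted cores, so in men positive on both tests a column with only one imaging test can count cancers found only in cores aimed at the other test's lesion

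*SAP*

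**What the plan says.** SAP 11.2.3 explains how the pathway table is filled. For each pathway, "we will take the population of participants with all positive tests along each pathway and provide summary statistics". MRI positivity means PIRADS 4 or 5, and ultrasound positivity uses the corresponding cut-off [2]. The summary statistics include "the total number of patients who were detected to have clinically significant cancer in targeted and non-targeted cores, separately", with the same split for insignificant cancer. The title of Table 1.2.14 repeats it: "detection of clinically insignificant cancer, in targeted and non-targeted cores, and clinically significant cancer, in targeted and non-targeted cores". Appendix 2 lists the histology variable "for targeted and non-targeted cores" and names no variable for the test that guided a core. Table 1 in SAP 11.2.1 agrees.

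SAP 10.3.5 treats targeted biopsy as one category. It counts patients "who undergo a targeted biopsy (MRI- and/or ultrasound-guided"). It then says who receives what: "A MRI or ultrasound-guided biopsy will be carried out for patients who receive a positive screening result by the respective test".

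Protocol 6.6 says that when imaging shows a lesion, "men will have image-fusion guided biopsies for each lesion detected". For men suspicious on both tests, Protocol 5.3.1 says "these men will be randomised to have their ultrasound or MRI targeted biopsies first in order to reduce incorporation bias". Such men therefore have cores aimed at both tests' lesions.

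**The concern.** A hypothetical pathway asks what would have been found had only its own tests been done. The MRI column takes in every man with PIRADS 4 or more, whatever his ultrasound showed. If he also had an ultrasound lesion, he has ultrasound-targeted cores that an MRI pathway would never have produced. A row labelled only as targeted cores gives the programmer no reason to leave them out. The Ultrasound column has the mirror-image problem, and the PSA & MRI and PSA & Ultrasound columns inherit it.

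The stake is the meaning of those rows. The table belongs to the primary outcome paper and serves the exploratory objective of comparing test combinations for a future study. Its targeted row should show what each test's own targeting found. A man who appears in both the MRI and the Ultrasound column would contribute the same targeted result to each, so the two columns are drawn together where a difference between the tests could show.

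**Working it through.** **Tracing one man through the table.** Take a man with PIRADS 4 and ultrasound score 4 at different sites and a PSA below 1.0. His MRI-targeted and systematic cores are benign, and his ultrasound-targeted cores show Gleason 3+4, which is significant under definition (i), the only definition used for the pathways.

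| Column, targeted row, significant cancer | As written | Counting only the pathway's own cores |
|---|---|---|
| MRI | 1 | 0 |
| Ultrasound | 1 | 1 |
| Ultrasound & MRI | 1 | 1 |

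The one-test MRI column changes; the column containing both tests does not.

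**Direction.** Definition (i) is met by Gleason 3+4 or higher in any core. Adding cores can turn a man from not significant to significant but never the reverse, so the significant-cancer count in the targeted row can only rise. The insignificant count can move either way: a man with 3+3 in MRI-targeted cores and 3+4 in ultrasound-targeted cores would leave that row.

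**Two further sources of pooling.** Targeting starts at score 3 (Protocol 6.3 and 6.4; SAP 8.2), but the pathways use 4 or more, so cores aimed at score-3 lesions enter the row as well. A lesion marked only by CAD/AI also leads to targeted biopsy (Protocol 6.3 and 6.6), although pathway positivity rests on the radiologist's PIRADS score.

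**Size.** The plan gives no figure for this effect. The base is its sample size, which reproduces: 1.96² × 0.611 × 0.389 / 0.05² = 365.2, rounded up to 366. The documents do not state how many men will score 4 or more (19.6% and 61.1% are for 3 or more), how many of those will also be ultrasound-positive, or how often cancer lies only in the other test's cores. All three are assumed here:

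- m, share of men with PIRADS 4 or 5: 10% to 20%
- u, share of those with ultrasound score 3 or more: 20% to 60%
- c, share of those double-positive men with significant cancer only in ultrasound-targeted cores: 2% to 10%

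Double-positive men = 366 × m × u. Men wrongly counted in the MRI column's targeted row = 366 × m × u × c.

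| m | u | Double-positive men | c = 2% | c = 5% | c = 10% |
|---|---|---|---|---|---|
| 10% | 20% | 7.3 | 0.15 | 0.37 | 0.73 |
| 10% | 60% | 22.0 | 0.44 | 1.10 | 2.20 |
| 20% | 20% | 14.6 | 0.29 | 0.73 | 1.46 |
| 20% | 60% | 43.9 | 0.88 | 2.20 | 4.39 |

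The smallest case is 366 × 0.10 × 0.20 × 0.02 = 0.15 men; the largest is 366 × 0.20 × 0.60 × 0.10 = 4.39 men.

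**The case against.** The plan nowhere says that the other test's cores are to be counted; it fails to say which targeted cores belong in which column. SAP 10.3.5 defines biopsy rates, not a rule for counting cancers, and its last sentence ties each guided biopsy to the respective test, which fits own-test counting. Figure 1 in SAP 8.3, which maps tests to biopsy, could not be read and may name the biopsy type per pathway. This stands as a limit on certainty. It does not remove the point, because the readable text, the table shell and the variable list that govern the programming carry no restriction.

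The Protocol's trial summary mentions targeted cores only for MRI lesions, which conflicts with Protocol 5.3.1 and 6.6 and with SAP 10.3.5. If no ultrasound-targeted cores were taken, the MRI columns would be free of them, but the targeted row of the Ultrasound column would then hold only cores aimed at MRI lesions (radiologist-scored or CAD/AI). The passages must be reconciled either way.

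Three stronger readings are tempting and are not supported:

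- A reader might infer that pooling hides the added yield of a second imaging test. Every pathway is a set of men positive on all its tests, and there is no either-positive column, so the table could not show added yield however the cores were labelled.
- A reader might put a percentage on the over-count. The documents give no expected number of cancers per column, so any percentage would rest on an invented denominator.
- A reader might conclude that results should be shown by randomised biopsy order. The stated reason for randomising is that the first lesion's tracts may influence the second's. Splitting 7 to 44 double-positive men by order would leave about 4 to 22 in each, too few to be informative.

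**Conclusion.** The point holds as a fault in how the table is specified. Read literally, the targeted-cores rows of the five columns with a single imaging test include cancers detected only through the other test's lesion, in men positive on both tests. For significant cancer the bias is upward only, and it tends to bring the MRI and ultrasound columns closer together. The columns that contain both imaging tests are not affected in this way.

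The size is unknown: from about zero to about 4 men in the MRI column, entirely on the assumptions above. It could be negligible. The end point is secondary and descriptive, with no hypothesis test, and the primary end point is untouched. The correction is still worth making before analysis, because it is cheap and the table is in the primary outcome paper. The conclusion would weaken if Figure 1 assigns a biopsy type to each pathway and that assignment governs the counting.

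**What to change.** In SAP 10.3.5, 11.2.3, Appendix 2 and Table 1.2.14:

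1. Classify each targeted core by the lesion it was aimed at: radiologist-scored MRI, ultrasound, or CAD/AI only.
2. In each column's targeted row, count only cores aimed at lesions that meet that pathway's own imaging test and cut-off (score 4 or more). This is a counting rule for the table and changes no biopsy.
3. Count cores aimed at a lesion seen on both tests under both.
4. Keep non-targeted cores as a separate row.

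Confirm that the biopsy form records the targeting source for each core. The allocated order implies that the source is known at the procedure, but the documents do not show that it is captured. Reconcile the Protocol's trial summary with Protocol 5.3.1 and 6.6 and SAP 10.3.5 on whether ultrasound lesions are targeted, and check the wording against Figure 1.

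The cost is SAP text, one derived variable and one table shell, plus a form check. Counts in the columns with one imaging test may come out slightly lower. Sample size and significance level do not change.
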